Hypothesis 2.2: Cartilage defects at or near the chondrolabral junction are prognostic indicators of worse outcomes as determined by the mHHS.

Hypothesis 2.3: Subjects with any degree of joint space narrowing (classified by Tonnis and Kellgren-Lawrence grading, see below) on plain radiographs will have more pain, regain less function, and do more poorly based on validated outcome measures, specifically the mHHS, at 6 and 12 months than subjects without any degree of joint space narrowing on plain radiographs.

EXPLORATORY Specific Aim 3: To evaluate the relationship between joint space narrowing on plain radiography and arthroscopically proven osteoarthritis.

Hypothesis 3.1: Tonnis grading and Kellgren-Lawrence grading on plain radiography are not predictive of the severity of arthritis at the time of arthroscopy.

Specific Aim 4: To analyze the data of subjects crossing over from PT alone to PT and surgery.

Hypothesis 4.1: Primary outcome scoring (mHHS) at 12 and 24 months after cross to surgery and PT will differ significantly from those initially randomized to surgical treatment.

Hypothesis 4.2: Baseline scores on outcome measures of those subjects crossing over will not differ significantly from those obtained at the time of crossover.

III. SUBJECT SELECTION & ENROLLMENT:

Study Overview: This is a prospective randomized control trial (RCT), which will enroll subjects with a clinically diagnosed tear of the acetabular labrum. Subjects who have been diagnosed with a labral tear in clinic will receive conservative physical therapy treatment alone or arthroscopic surgical labral repair and physical therapy. If it is discovered that there is unexpected pathology at the time of arthroscopy for subjects in the surgery group, those subjects will be removed from the study. This is due to the possibility that the source of pain is less likely a result of the dysfunction of the labrum and more likely due to aberrant extra-articular biology. We will use validated outcomes measures that include the mHHS, LEFS, HOS, NAHS, and iHOT-33 (see below) and review the medical record for physical exam findings to track patient progress throughout their involvement in the study which will continue for as long as they are a patient of the PI. Study procedures will be complete when the last enrolled subject completes 24-month follow-up and completes the corresponding surveys.

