Our Primary Outcome is change in the modified Harris Hip Score at 12 months and 24 months. Secondary outcomes include changes in other validated outcomes measures patient satisfaction, and degree of improvement on physical exam. The influence of OA severity (Outerbridge scoring) and location of OA will also be analyzed to determine if they have an effect on the aforementioned outcome measures. Satisfaction will be assessed by an exit questionnaire (See section IV). In addition to gauging satisfaction, this questionnaire will ask subjects how they felt about their participation in the study. (See section IV)

Inclusion and Exclusion Criteria:

Inclusion criteria	Rationale
Age 40 or greater	Higher likelihood of undetectable OA on imaging
Orthopedic surgeon determines symptoms are consistent with a labral tear.	Required for treatment
Availability of hip radiographs and MRI	Needed to assess eligibility and comparison for specific aim 3
Willingness to undergo randomization and ability to understand and sign informed consent document	Ability to understand study and consent willingly

Exclusion criteria	Rationale
Unexpected pathology at the time of arthroscopy	Source of pain less likely to due dysfunction of the labrum and more likely due to aberrant extra-articular biology
Same site surgery	Complex anatomy
Contraindication to surgery or physical therapy	Cannot tolerate either treatment grouping
Alternate form of PT for greater than 6 weeks	Will negatively augment results. May affect recruitment.

Selection and enrollment:

We will enroll 122 consecutive subjects meeting the aforementioned criteria. Subjects will be randomized into conservative or surgical treatment arms. All potential subjects on the clinic schedule of the investigator will be pre-screened for eligibility based on age, clinical assessment, and previous medical history.

All eligible subjects will be approached at an outpatient clinic visit. Those who initially meet inclusion criteria will be introduced to the study and given a research consent form that they have the opportunity to take home and to review.

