The research coordinator will randomize the subjects into the study at this visit. Randomization will be assigned utilizing an electronic randomization program. Those receiving conservative management will be scheduled for physical therapy. Those receiving surgical management will be scheduled for surgery and the post-operative physical therapy protocol within 2 weeks of their operative date.

Efforts will be made to attain a mix of study participants, regarding gender and racial/ethnic representation reflective of the population of the greater metropolitan Boston area: 66% White, 14% African American and 10% Hispanic or Latino. More specifically, we anticipate that at least half of our subjects will be female and that we will have representation from Asian American, African American and Hispanic minority groups in our final cohorts.

Informed consent:

The informed consent document will be approved by the IRB at Partners HealthCare, which covers The Brigham and Women's Hospital, Faulkner Hospital, and the Brigham and Women's/Mass General Health Care Center at Foxborough. The informed consent process will be conducted by the PI.

Overview of sample size:

This randomized control trial includes 122 subjects age 40 or older with evidence consistent with tears of the acetabular labrum in the affected hip

Meeting recruitment targets:

As previously mentioned, the design of our study is similar to that of the MeTeOR trial ⁴³ in which [name] and [name] were lead investigators. [name] was the highest referral base for the

MeTeOR subjects at the BWH site and [name] designed, delivered and managed the physical therapy protocol for both arms of the MeTeOR trial across 7 national trial centers. Based on a survey before that trial commenced, it was estimated that 20-25% of eligible subjects would agree to participate in the randomized controlled trial. Participation in the actual trial was 26%. We anticipate a similar recruitment percentage as our design is similar as are our inclusion criteria.

Study retention procedures:

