[name] and [name] were investigators in a similarly designed multicenter trial involving meniscal tears in the knee.⁴³ In that recently published study, once enrolled, the patient retention rate was approximately 90%. We believe we will have similar success over the course of this study. Nevertheless, procedures will be in place to aid in maintaining subject participation over the course of the study. Outcome measures collected around formal visits can be collected remotely. Subjects can receive the surveys via email sent through REDcap. Study staff will conduct reminder phone calls around data collection time points.

IV. STUDY PROCEDURES:

Enrolled subjects will complete surveys around normal clinic visit intervals. Subjects will continue receiving surveys around their normal postoperative clinic visits until they request to stop receiving them. We are interested in long-term outcomes for these treatment arms, so we hope to collect patient-reported outcome measures for several years after randomization. These surveys can be completed remotely or at clinic visits. Follow up/reminder calls will be conducted to ensure subjects complete surveys.

Medical History:

The medical record may be reviewed for relevant medical history, imaging, physical exam, and surgical procedure from the subject's operative note, imaging, or clinic visit notes.

Patient-Reported Outcome Measures (PROMs) Surveys:

Pain/Physical Function:

Modified Harris Hip Score (mHHS): The MHHS is a validated condition specific outcome instrument that is used widely after hip arthroscopy. The eight questions measure domains of pain, gait function, and functional activities. Scores range from 0 (poor) to 100.1 (ideal).^{45,46}

The Lower Extremity Function Scale (LEFS): The LEFS is a 20 item validated outcome measure that is commonly used by physical therapists to initially evaluate and subsequently monitor patient progress through the course of a rehabilitation program. The minimum level of detectable change is 9 points.⁴⁷

Hip Outcome Score (HOS): The HOS is composed of the activities of daily living (HOS-ADL) subscale and the sports (HOS-sports) subscale. The HOS-ADL subscale contains 19 items pertaining to basic daily activities, and the HOS-sports subscale contains 9 items pertaining to higher-level activities, such as those required in athletics. In addition to the 5 potential responses, ranging from "unable to do" to "no

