The mean outcome scores of the mHHS in each treatment group at 12 months will be compared to baseline scores to assess for significant differences using paired sample t-test in SPSS 16 (SPSS, Chicago, IL). The mean outcomes scores of the mHHS between groups at 12 months will be compared using independent t-tests to assess for significant difference. We will use a Levene test to judge variance and proceed accordingly. If a statistically significant difference is detected during these analyses, we will calculate the effect size (ES) to determine how meaningful these results are outside of being statistically significant. The ES will be calculated by: [(mean mHHS score of surgical arm / mean mHHS of the conservative group) / standard deviation of the conservative group]. According to Cohen ⁵⁸, an ES <0.1 is trivial, ES of 0.1-0.3 is minimal, ES of 0.3-0.5, is moderate, and ES >0.5 is large. We will repeat the same analysis at 12 months.

Hypothesis 2.1, 2.2, and 2.3:

Diagnosis and treatment of the prearthritic and early arthritic hip has been an area of intense interest. However, our most conventional method of assessment (plain radiography) does not provide us with enough diagnostic sensitivity.⁴¹ Direct visualization on the articular surfaces in the hip is both sensitive and specific. Furthermore, emphasis is being placed on the location of arthritis as a prognostic indicator of good outcomes following hip arthroscopy. The value of arthroscopic techniques for primary

symptoms and/or prevention of OA secondary to labral tears remains unclear even though preliminary reports indicate there may be some benefit to repairing a torn labrum, even in cases of severe OA. Evaluation of arthritic change at the time of arthroscopy is important, particularly in subjects where there remains uncertainty about the efficacy of labral repair for those with articular or rim cartilage degeneration that the effects of those changes on long-term OA progression.⁵⁹

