Using the data from our retrospective review of outcomes following labral repair, a 10 point or greater difference on the mHHS as significant, and a single-tail independent t-test to evaluate the difference between means with 80% power and a 5% significance level, 35 subjects are needed to demonstrate a statistically significant difference between the average mHHS of the conservative group and surgical group. Testing of hypothesis 1.5 will be an intragroup analysis looking for a significant difference in outcome measures from the time of completion of PT (non-crossover) when compared to the same data to be collected at 12 months and 24 months. The purpose is to determine the short-term durability of the response to PT, if one is found.

70 study completers should provide us with the necessary data needed to substantiate or reject our hypothesis. There has been no prospective trial to date testing these hypotheses in the hip, but we expected a 7.3-10.3% dropout rate based on the results of a similar study in the knee. However, as of July 2018, we had 47 patients that had passed the 2-year follow-up mark, of which 5 patients were no longer in the study (combination of lost to follow-up and proceeding to total hip arthroplasty), and another 11 had yet to complete their 2-year surveys even with multiple attempts to contact them and encourage them to do so. With a yield of 31 patients out of 47, or 65.95%, we increased our sample size to 122.

Therefore, we estimate needing 122 subjects to achieve 70 study completers, in the appropriate proportion of 35 subjects per treatment arm. We enroll until reaching at least 35 subjects in each group.

The results of the MeTeOR trial in the knee show that we can expect a higher drop-out rate in the surgical group. As such, this cohort may be our limiting factor.^{40, 43, 61, 62}

Specific Aim 2. Hypotheses 2.1-2.3: *To evaluate the significance of arthritic burden on short term outcomes following arthroscopic labral repair.*

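### Surgery-arm subjects are removed after randomisation for a finding made only at arthroscopy, so Hypothesis 1.3 does not compare the groups as randomised

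*Combined protocol and SAP*

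**What the plan says.** - **Timing of randomisation** (section III, Selection and enrollment): "The research coordinator will randomize the subjects into the study at this visit". This is an outpatient clinic visit, and surgery is scheduled afterwards.
- **Removal rule** (section III, Study Overview): if there is "unexpected pathology at the time of arthroscopy for subjects in the surgery group, those subjects will be removed from the study". The reason given is: "This is due to the possibility that the source of pain is less likely a result of the dysfunction of the labrum".
- **Exclusion table** (section III, Inclusion and Exclusion Criteria): the first row reads "Unexpected pathology at the time of arthroscopy". This row is not limited to one arm. The term is not defined in either place.
- **Analysis** (section V, Hypothesis 1.1-1.4): "The mean outcomes scores of the mHHS between groups at 12 months will be compared using independent t-tests to assess for significant difference". No analysis set is named.
- **Sample size** (section V, Power Analysis): the calculation uses "a single-tail independent t-test to evaluate the difference between means with 80% power and a 5% significance level", and "70 study completers should provide us with the necessary data needed to substantiate or reject our hypothesis". Enrolment continues until each group has at least 35.
- **Crossover** (section IV, Physical Therapy Visits, and section VIII, item 1a): PT subjects may move to surgery, officially from 6 weeks after enrolment.
- **Follow-up** (section III, Study retention procedures): "Outcome measures collected around formal visits can be collected remotely".

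**The concern.** Hypothesis 1.3 is the main between-arm question, and Hypothesis 1.4 carries it to 24 months. Randomisation protects that comparison only if membership of each arm is fixed at randomisation, or if any later exclusion applies equally to both arms. This exclusion cannot do so, because it depends on a finding that one arm's treatment reveals and the other's does not. Subjects with the same pathology in the PT arm remain and contribute to the PT mean.

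The plan's own reason for removal suggests which way this leans. If these subjects' pain is less likely to come from the labrum, they are plausibly poorer responders to labral repair. Taking them out of the surgery arm alone would then flatter surgery. Because the term is undefined, each removal also rests on a judgement made by an unblinded surgeon during the operation.

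**Working it through.** **1. Does the text lead to exclusion from the analysis?** The Study Overview does not expressly say that data already collected are discarded. Against that:
- the subject is removed from the study;
- the same finding is an exclusion criterion;
- the sample size is stated in completers;
- enrolment runs until the per-group target is met, so a removed subject can be replaced;
- no section mentions intention-to-treat, an as-randomised set, or follow-up of removed subjects.

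The plan states no route by which these subjects return to the comparison.

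**2. Can the PT arm be treated alike?** Only PT subjects who cross over reach arthroscopy. The Study Overview confines removal to the surgery group, while the exclusion row does not, so the handling of crossovers is unclear. Under either reading, PT subjects who never have arthroscopy are untouched.

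**3. Implied SD.** The plan gives 35 per arm, 80% power, 5% significance and a 10-point difference, but no SD. Solving backwards with the noncentral t distribution (68 df):
- One-sided: standardised difference 0.600, SD = 10/0.600 ≈ 16.66, standard error = 16.66 × √(2/35) = 3.98.
- Two-sided: standardised difference 0.679, SD ≈ 14.72, standard error = 3.52.

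These SDs are inferred from the plan's figures, so the 35 per arm cannot be independently confirmed.

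**4. Size of the shift (illustration).** Let *r* be the share of the surgery arm removed and *g* the amount by which their mean mHHS would have fallen below that of the retained subjects. With no true effect, the PT mean still contains the share *r*, so the difference shifts toward surgery by *r* × *g*. Both *r* and *g* are assumptions.

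| r | g (points) | Shift (points) | One-sided 5% error, SD 16.66 | Two-sided 5% error, SD 16.66 | Two-sided 5% error, SD 14.72 |
|---|---|---|---|---|---|
| 5% | 10 | 0.5 | 6.4% | 5.2% | 5.2% |
| 10% | 10 | 1.0 | 8.1% | 5.7% | 5.9% |
| 10% | 20 | 2.0 | 12.6% | 7.9% | 8.7% |

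If the 122 are split equally, 5% to 10% of 61 is about 3 to 6 subjects.

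**5. Partial matching through crossover.** If a share *c* of the affected PT subjects cross over and are also removed, the shift is g·r·(1−c)/(1−r·c). With r = 0.10, g = 10 and c = 0.5, this is 10 × 0.10 × 0.5/0.95 = 0.53 points, or 6.5% one-sided.

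**6. Reverse case.** If the removed subjects would have done 10 points better, the same 10% gives a shift of −1.0 point, and the one-sided error falls to about 3%.

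**7. Do the documents hint at the removal rate?** The Power Analysis accounts for 47 patients past 2 years as 31 with data, 5 no longer in the study (lost to follow-up or hip replacement) and 11 with outstanding surveys: 31 + 5 + 11 = 47. No removal for pathology is mentioned. If about 23 of the 47 were in the surgery arm (the split is not given), the chance of no removals is 0.95^23 = 31% at a 5% rate, 0.90^23 = 9% at 10% and 0.85^23 = 2% at 15%. The one-sided 95% upper limit is 1 − 0.05^(1/23) = 12.2%. This carries little weight, since removed subjects may have been dropped before the 47 were counted.

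**The case against.** The strongest reply has four parts.

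- **The loss is inferred.** The plan never says that removed subjects' scores are left out; completers appear in the sample-size text, not in the test. This is fair as a description of the wording. But removal from the study, with no set that brings these subjects back, makes exclusion the natural reading. If the sponsor intends otherwise, one sentence would settle it.
- **Some PT subjects may be removed too.** The exclusion row could reach crossovers. This stands and would reduce the imbalance, but it cannot restore balance for PT subjects who never have surgery.
- **Direction and size are unproven.** This stands. The pathology is undefined, no outcomes are given, and the bias would reverse if removed subjects would have fared better. At the low end of the illustration the error rate barely moves. Section V does not state the sidedness of the test, and the larger error rates assume the one-sided test of the Power Analysis.
- **Past removals may be beyond repair.** The documents report none. If there were any, a 12-month score that was never collected cannot be obtained by later contact. This limits what the remedy can recover but is no reason to keep the rule.

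How crossovers are analysed is a related gap, but the severity here does not depend on it.

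**Conclusion.** The concern holds, and the plan must be changed. A stated rule takes subjects out of one arm after randomisation, on a finding that the other arm largely cannot show. Nothing elsewhere in the plan restores the randomised comparison for Hypothesis 1.3.

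The severity rests on that structural fault and not on the illustrative figures. Under assumed removal of 5% to 10% with a 10- to 20-point deficit, the shift is 0.5 to 2.0 mHHS points. The error rate is then about 6% to 13% one-sided, or 5% to 9% two-sided, against a nominal 5%. The true rate, deficit and direction are unknown. The conclusion assumes that removed subjects do not enter the t-test, which is how the text reads although it is not said outright.

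**What to change.** 1. **Section III, Study Overview and exclusion table.** Delete the removal and the matching exclusion row for purposes of study participation and analysis. Clinical care of these subjects is not affected.
2. **Follow-up.** Keep surveying these subjects on the same schedule, using the remote collection already provided for.
3. **Section V, Hypothesis 1.1-1.4.** State that the primary between-arm comparison includes all randomised subjects in their assigned arm, including those who cross over from PT to surgery.
4. **Reporting.** Give the number of unexpected-pathology cases, and of any removals already made, by arm. Report 12-month scores that were not collected as missing.
5. **Sensitivity analysis.** Present the analysis without unexpected-pathology cases only in this role, noting that such cases cannot be identified in PT subjects who never have arthroscopy.

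The cost is a wording change in three places, a few more remote surveys, and possible re-contact of subjects already removed where consent allows. The estimated effect of surgery may be smaller than under the present rule.

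### The protocol gives three conflicting ends of participation and ties surveys to postoperative visits, so on one reading collection of the 12- and 24-month mHHS can depend on treatment and result

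*Combined protocol and SAP*

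**What the plan says.** The primary outcome is stated in Section III, Study Overview: "Our Primary Outcome is change in the modified Harris Hip Score at 12 months and 24 months". The time from which those months are counted is not stated there.

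Three statements bear on how long a subject is followed:

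- Section III, Study Overview: the outcome measures and record review will "track patient progress throughout their involvement in the study which will continue for as long as they are a patient of the PI".
- The next sentence of the same section: "Study procedures will be complete when the last enrolled subject completes 24-month follow-up and completes the corresponding surveys".
- Section IV, opening paragraph: "Subjects will continue receiving surveys around their normal postoperative clinic visits until they request to stop receiving them".

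On timing and mode, Section IV also says "Enrolled subjects will complete surveys around normal clinic visit intervals" and "These surveys can be completed remotely or at clinic visits". Section III, Study retention procedures, adds "Subjects can receive the surveys via email sent through REDcap" and plans reminder telephone calls. Section IV hopes for several years of data counted from randomisation. Aim 4 uses a different clock, 12 and 24 months after crossover.

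On losses so far, Section V (Power Analysis, Specific Aim 1) reports 47 subjects past two years as of July 2018. Five were out of the study, through a mixture of loss to follow-up and progression to total hip arthroplasty, and "another 11 had yet to complete their 2-year surveys even with multiple attempts to contact them". The same section expects more dropout in the surgical arm. Section V compares mean mHHS by t-test and gives no method for missing outcomes.

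**The concern.** The three statements cannot all define the end of follow-up. If the first governs, a subject who leaves the surgeon's care leaves the study, and whether someone stays in that care can depend on the treatment received and on how it went. The survey sentence is written for operated subjects. A subject who stays on physical therapy alone has no postoperative visit, and neither does a subject assigned to surgery who never has it.

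The arthroplasty remark matters more than the wording. It shows that at least one subject with a poor course has been counted as out of the study. Section VIII, item 1a, also offers leaving the study to physical-therapy subjects who do not want to wait for official crossover, and does not say whether outcome collection would continue.

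If outcomes are missing for reasons tied to arm and result, the subjects compared at 12 and 24 months are no longer the groups that were randomised. A t-test on the available scores does not correct for that, and neither does enrolling more subjects, which is how the plan responded to the losses.

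**Working it through.** **The statements side by side.** Being the PI's patient can end before 24 months or long after. A request to stop can come at any time. The 24-month sentence defines when study procedures finish, not when one subject's follow-up ends. No sentence says which prevails, and no 12- or 24-month window is counted from randomisation for the primary comparison.

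**The plan's own yield** (Section V, Power Analysis):

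- Completers: 47 − 5 − 11 = 31, and 31/47 = 65.96%. The plan prints 65.95%, so the figure reproduces apart from truncation. The exact 95% interval for the yield is 51% to 79%.
- Missing at two years: 16/47 = 34.0%, made up of 5/47 = 10.6% out of the study and 11/47 = 23.4% without a survey. Non-response is therefore 11/16 = 69% of the loss. The plan had expected 7.3–10.3% dropout.
- No split by arm and no 12-month figure is given. The split of the five between loss to follow-up and arthroplasty is not given either.

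**Possible bias.** Let m be the fraction missing in an arm and g the difference in mean mHHS between responders and non-responders in that arm. The responder mean is off by m × g, so the contrast is off by m(surgery) × g(surgery) − m(PT) × g(PT). Every value of g below is an assumption, because the documents give none.

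- Equal m and equal g in both arms: bias 0.
- m = 0.340 in each arm, g = 5, 10 or 15 in one arm and 0 in the other: 0.340 × 5 = 1.7, 0.340 × 10 = 3.4, 0.340 × 15 = 5.1 points.
- Missing 43% in one arm and 25% in the other (average 34%), g = 10 in both: (0.43 − 0.25) × 10 = 1.8 points. The sign depends on which arm loses more and whether non-responders do better or worse.

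**What a bias of that size would do.** The power analysis uses a 10-point difference, a one-sided 5% test, 80% power and 35 per arm. It states no SD. Solving for it: 10 / [(1.645 + 0.842) × √(2/35)] ≈ 16.8. The standard error of the contrast is then 16.8 × √(2/35) ≈ 4.02.

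- Bias favouring surgery by 1.7, 3.4 or 5.1 points: the one-sided type I error rises from 5% to about 11%, 21% or 35%.
- Bias against surgery by the same amounts, with a true 10-point difference: power falls from 80% to about 66%, 50% or 34%.

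**Most that better collection could recover.** If all 11 non-responders gave an mHHS, the yield would be (31 + 11)/47 = 89% and the missing fraction 5/47 = 10.6%. The one-arm shifts above would then be 0.5, 1.1 and 1.6 points. This is an upper bound, since repeated contact had already failed with these 11.

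**The case against.** The strongest reply is that the protocol does not need clinic attendance to collect outcomes. Surveys may be completed remotely, go out by email and are backed by reminder calls, none of it limited by arm. The general survey sentence covers all enrolled subjects. Section IV also says that subjects will be seen in clinic, and it sends the satisfaction questionnaire yearly from about one year without restriction to operated subjects. The clause about being the PI's patient can be read as open-ended follow-up beyond 24 months, and nowhere does the protocol say that surveys stop when a subject leaves the practice. This stands. It is why the point is a conflict in the documents and not a demonstrated withdrawal rule.

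A reader might infer more: that recovered physical-therapy subjects drift away while operated subjects stay, so that loss is already driven by arm. The documents do not support that. None of the 16 missing results is attributed to leaving the PI's care. Eleven were being actively pursued, and some may simply have been late in July 2018. No loss is reported by arm, and the sponsor expects more dropout in surgery, the opposite of that account. Section IV (Physical Therapy Visits) does mention a patient who seeks a surgeon elsewhere, but explicitly outside a study, and contrasts this with subjects who are already known to the surgeon.

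The sponsor might also say that an mHHS after hip replacement no longer measures the assigned treatment. That is a question about how the score is used. It is no reason to leave it uncollected, and the analysis section does not address it.

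What remains is the unreconciled wording, a survey sentence that does not fit subjects who are not operated on, the exit after arthroplasty, and the absence of a missing-data method.

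**Conclusion.** The concern holds as a conflict that leaves the primary outcome exposed; it is not a finding of bias. The documents give three ends of participation and a schedule partly written for operated subjects. They count subjects as out of the study after arthroplasty, and 34% had no 2-year data. Collection can therefore depend on treatment and result on one reading of the text.

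The size and direction of any bias are unknown. The range runs from zero to about 5 points against a 10-point target. The upper end rests on an assumed 15-point gap confined to one arm, with the pooled 24-month loss applied to that arm. The error rates and power figures also rest on a back-solved SD of 16.8. Nothing here can be carried over to 12 months, for which no loss is reported. The correction is cheap and should be made.

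**What to change.** Replace the clause in Section III that ties involvement to being the PI's patient with:

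> Every randomised subject is followed for mHHS to 24 months from randomisation, whether or not they received or stopped the assigned treatment, crossed over, had hip arthroplasty, changed surgeon, or remain a patient of the PI; only withdrawal of consent ends collection.

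Then:

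- Reconcile that sentence with the removal from the study for unexpected pathology at arthroscopy (Section III, Study Overview and exclusion criteria), and bring the Section IV survey sentences into line with it.
- Send the REDCap surveys at 12 and 24 months from randomisation in both arms. Keep the post-crossover time points for Aim 4 as a separate schedule.
- When the full battery is not returned, take the eight-question mHHS in the reminder call already planned, ask about hip surgery elsewhere, and record the mode of collection.
- State in Section V how subjects still without an mHHS, and scores obtained after arthroplasty, enter the comparison. Report losses by arm and time point, with a sensitivity analysis over a range of assumed gaps in each arm.

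The cost is protocol wording, a REDCap calendar change and somewhat longer reminder calls, with no new staff or visits. The downside is a mix of self-completed and telephone scores, which is why the mode must be recorded. How many non-responders this would recover is unknown; the documents do not say why they did not reply.
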